**Table E12 CYP3A Inducers**

Strong inducers of CYP3A	Moderate inducers of CYP3A
Carbamazepine	Bosentan

**Table E12 CYP3A Inducers**

Strong inducers of CYP3A	Moderate inducers of CYP3A
Enzalutamide	Efavirenz
Mitotane	Etravirine
Phenytoin	Modafinil
Rifampin	
St. John's wort a	

a The effect of St. John's wort varies widely and is preparation-dependent.

Source: US FDA. Drug development and drug interactions: table of substrates, inhibitors and inducers.

<http://www.fda.gov/Drugs/DevelopmentApprovalProcess/DevelopmentResources/DrugInteractionsLabeling/ucm093664.htm#inVivo>. Accessed 23 July 2019.

**Table E13 Other Drugs Needing Additional Considerations**

Proton pump inhibitors	H2-receptor antagonists
Dexlansoprazole	Cimetidine
Esomeprazole	Famotidine
Lansoprazole	Nizatidine
Omeprazole	
Rabeprazole	
Pantoprazole	

Source: US FDA. Established pharmacologic class text phrase. <https://www.fda.gov/downloads/drugs/guidancecomplianceregulatoryinformation/lawsactsandrules/ucm428333.pdf>. Accessed 23 July 2019.

## Appendix F Contraception Requirements

Contraception requirements for this study are described below.

### F 1 Female Participants of Childbearing Potential

Please note, females of childbearing potential are defined as those who are post-menarche, not surgically sterile (ie, bilateral salpingectomy, bilateral oophorectomy, or complete hysterectomy) or post-menopausal.

Women will be considered postmenopausal if they have been amenorrheic for 12 months without an alternative medical cause. The following age-specific requirements apply:

- Women <50 years of age would be considered postmenopausal if they have been amenorrheic for 12 months or more following cessation of all hormonal replacement therapy and if they have luteinizing hormone and follicle-stimulating hormone levels in the postmenopausal range for the institution.
- Women  $\geq$ 50 years of age would be considered postmenopausal if they have been amenorrheic for 12 months or more following cessation of all hormonal replacement therapy, had radiation-induced menopause with last menses >1 year ago, had chemotherapy-induced menopause with last menses >1 year ago.

Female participants of childbearing potential who are not totally sexually abstinent (ie, refraining from heterosexual intercourse during the entire period of risk associated with study intervention), and who intend to be sexually active with a nonsterilized male partner, must use  $\geq$  1 highly effective method of contraception (see Table F14) consistent with local regulations regarding the use of contraception for participants participating in clinical trials, from the time of signing the ICF throughout the total duration of the drug treatment and the drug washout period (2 days after the last dose of acalabrutinib).

Non-sterilized male partners of a female participant of childbearing potential must use a male condom plus spermicide (condom alone in countries where spermicides are not approved) throughout this period. Cessation of birth control after this point should be discussed with a responsible physician. Periodic abstinence, the rhythm method, and the withdrawal method are not acceptable methods of contraception. The reliability of total sexual abstinence should be evaluated in relation to the duration of the clinical trial and the preferred and usual lifestyle of the participant. Female participants should refrain from breastfeeding throughout this period.

## **F 2 Male Participants with a Female Partner of Childbearing Potential**

Non-sterilized male participants (including males sterilized by a method other than bilateral orchidectomy, eg, vasectomy) who are not abstinent and intend to be sexually active with a female partner of childbearing potential must use a male condom plus spermicide (condom alone in countries where spermicides are not approved) from the time of screening throughout the total duration of the drug treatment and the drug washout period (2 days after the last dose of acalabrutinib). Periodic abstinence, the rhythm method, and the withdrawal method are not acceptable methods of contraception. Male participants should refrain from sperm donation throughout this period.

Vasectomized (ie, sterile) males are considered fertile and should still use a male condom plus spermicide as indicated above during the clinical trial.

Even if the female partner is pregnant, male participants should still use a condom, as indicated above during the clinical trial, if there is a concern about damaging the developing fetus from drug in ejaculate.

Female partners (of childbearing potential) of male participants must also use a highly effective method of contraception throughout this period (see Table F14).

## **F 3 Highly Effective Methods of Contraception**

Highly effective methods of contraception, defined as one that results in a low failure rate (ie, less than 1% per year) when used consistently and correctly, are described in Table F14. Note that some contraception methods are not considered highly effective (eg, male or female condom with or without spermicide; female cap, diaphragm, or sponge with or without spermicide; non copper containing intrauterine device; progestogen-only oral hormonal contraceptive pills where inhibition of ovulation is not the primary mode of action [excluding Cerazette/desogestrel, which is considered highly effective]; and triphasic combined oral contraceptive pills).

**Table F14 Highly Effective Methods of Contraception (<1% Failure Rate)**

Barrier/intrauterine methods	Hormonal methods

 
• Copper T intrauterine device
 
• Levonorgestrel-releasing intrauterine system (eg, Mirena®)a
 
	
 
• Implants: Etonogestrel-releasing implants (eg, Implanon® or Norplant®)
 
• Intravaginal devices: Ethinylestradiol/etonogestrel-releasing intravaginal devices (eg, NuvaRing®)
 
• Injection: Medroxyprogesterone injection (eg, Depo-Provera®)
 
• Combined pill: Normal and low dose combined oral contraceptive pill
 
• Patch: Norelgestromin/ethinylestradiol-releasing transdermal system (eg, Ortho Evra®)
 
• Minipill: Progesterone based oral contraceptive pill using desogestrel: Cerazette is currently the only highly effective progesterone-based pill
 

a This is also considered a hormonal method.

## Appendix G Child-Pugh Score

Cirrhosis severity, as determined by the Child-Pugh score, will be recorded in the eCRF as specified in the SoA (Table 1).

The modified Child-Pugh classification of liver disease severity according to the degree of ascites by clinical exam, serum concentrations of bilirubin and albumin, prothrombin time, and degree of encephalopathy is shown in Table G15. The severity of cirrhosis is classified as follows:

- Child-Pugh class A (well-compensated disease): score of 5 to 6
- Child-Pugh class B (significant functional compromise): score of 7 to 9
- Child-Pugh class C (decompensated disease): score of 10 to 15

**Table G15 Child-Pugh Classification of Cirrhosis Severity**

Parameter	Points assigned		
	1	2	3
Ascites	Absent	Slight	Moderate
Bilirubin	<2 mg/dL (<34.2 µmol/L)	2 to 3 mg/dL (34.2 to 51.3 µmol/L)	>3 mg/dL (>51.3 µmol/L)
Albumin	>3.5 g/dL (35 g/L)	2.8 to 3.5 g/dL (28 to 35 g/L)	<2.8 g/dL (28 g/L)
Prothrombin time			
Seconds over control	<4	4 to 6	>6
INR	<1.7	1.7 to 2.3	>2.3
Encephalopathy	None	Grade 1 to 2	Grade 3 to 4

INR = international normalized ratio.

## Appendix H Proton-pump Inhibitor Equivalence Table

Table H16 shows the PPI doses relating to evidence synthesis and recommendations in the original NICE clinical guidelines.

**Table H16 Proton-pump Inhibitor Doses Relating to Evidence Synthesis and Recommendations in the Original Guideline (CG17; 2004)**

Proton-pump inhibitor	Full/standard dose	Low dose (on-demand)	Double dose
Esomeprazole	20 mg a once daily	Not available	40 mg c once daily
Lansoprazole	30 mg once daily	15 mg once daily	30 mg b twice daily
Omeprazole	20 mg once daily	10 mg b once daily	40 mg once daily
Pantoprazole	40 mg once daily	20 mg once daily	40 mg b twice daily
Rabeprazole	20 mg once daily	10 mg once daily	20 mg b twice daily

a Lower than the licensed starting dose for esomeprazole in GERD, which is 40 mg, but considered to be dose-equivalent to other PPIs. When undertaking meta-analysis of dose-related effects, NICE classed esomeprazole 20 mg as a full-dose equivalent to omeprazole 20 mg.

b Off-label dose for GERD.

c 40 mg is recommended as a double dose of esomeprazole because the 20-mg dose is considered equivalent to omeprazole 20 mg.

GERD = gastroesophageal reflux disease; NICE = National Institute for Health and Care Excellence; PPI = proton-pump inhibitor.

Proton-pump inhibitors listed in Table H17 may be used more frequently in the ICU setting and are allowed on study.

**Table H17 Proton-pump Inhibitors Allowed in Intensive Care Unit**

Medication	Route	Dose in the ICU
Esomeprazole	PO NG or IV	40 mg daily
Lansoprazole	PO NG or IV	15 or 30 mg daily
Omeprazole	PO NG or IV	20 to 40 mg daily
Pantoprazole	PO NG or IV	40 mg daily

ICU = intensive care unit; IV = intravenously; NG = nasogastric; PO = orally.

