### Overall Design

This is an open-label, multi-dose study to evaluate the PK, and safety and tolerability of acalabrutinib suspension, when coadministered with a PPI, in participants with confirmed SARS-CoV-2 infection requiring hospitalization due to respiratory failure (as defined in the table above) attributable to COVID-19 pneumonia and who have an NG tube in place. Approximately 20 participants will be included to ensure at least 16 participants are evaluable. Participants are considered evaluable if they have an evaluable PK profile, ie: (1) complete PK Visit 2 assessments; (2) receive active treatment; and (3) do not have unavailable or

incomplete data that may influence the PK analysis.

In addition to receiving BSC, participants will receive acalabrutinib suspension (ie, acalabrutinib 100 mg suspension in COCA-COLA® delivered via NG tube) bid for 14 days (a maximum of 28 doses). Best supportive care is per discretion of the Investigator and institutional guidelines. Standard NG tubes supplied by the hospital will be used. Nasogastric tube placement in the stomach will be confirmed by chest x-ray.

To assess the effect of PPIs, all participants must be receiving treatment with a PPI at the start of the study. Treatment with a PPI can begin at any time prior to enrollment, provided participants have received PPI treatment for at least 24 hours prior to the first dose of acalabrutinib suspension. Any PPI is permitted, provided it meets the minimum equivalent daily dose of 20 mg rabeprazole. Participants must be on this dosage of PPI at the start of the study. They may be weaned off PPIs during the study if medically appropriate.

Blood samples for plasma PK assessment of acalabrutinib and its metabolite (ACP-5862) will be collected at pre-dose and 0.5, 1, 2, 4, 6, and 12 hours following treatment with acalabrutinib suspension as described in the table below. Note that the sample at 12 hours must be collected prior to the subsequent acalabrutinib dose (for trough PK sample).

PK Visit	Description	Rationale
PK Visit 1	First PK sampling will occur on Day 1 (ie, first dosing day for acalabrutinib suspension)	Allows an early assessment of acalabrutinib and ACP-5862 PK in participants receiving acalabrutinib suspension via NG tube

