## 4 STUDY DESIGN

### 4.1 Overall Design

This is an open-label, multi-dose study to evaluate the PK, and safety and tolerability of acalabrutinib suspension, when coadministered with a PPI, in participants with confirmed SARS-CoV-2 infection requiring hospitalization due to respiratory failure (as defined in Section 8.1.1.1) attributable to COVID-19 pneumonia and who have an NG tube in place. Approximately 20 participants will be included to ensure at least 16 participants are evaluable. Participants are considered evaluable if they have an evaluable PK profile, ie: (1) complete PK Visit 2 assessments; (2) receive active treatment; and (3) do not have unavailable or incomplete data that may influence the PK analysis.

In addition to BSC, participants will receive acalabrutinib suspension (ie, acalabrutinib 100 mg suspension in COCA-COLA delivered via NG tube) bid for 14 days (a maximum of 28 doses). Best supportive care is per discretion of the Investigator and institutional guidelines. Standard NG tubes supplied by the hospital will be used. Nasogastric tube placement in the stomach will be confirmed by chest x-ray.

To assess the effect of PPIs, all participants must be receiving treatment with a PPI at the start of the study. Treatment with a PPI can begin at any time prior to enrollment, provided participants have received PPI treatment for at least 24 hours prior to the first dose of acalabrutinib suspension (Figure 1). Any PPI is permitted, provided it meets the minimum equivalent daily dose of 20 mg rabeprazole (Appendix H). Participants must be on this dosage

of PPI at the start of the study. They may be weaned off PPIs during the study if medically appropriate.

Blood samples for plasma PK assessment of acalabrutinib and its metabolite (ACP-5862) will be collected at pre-dose and 0.5, 1, 2, 4, 6, and 12 hours following treatment with acalabrutinib suspension as described in Table 4 below and illustrated in Figure 1. Note that the sample at 12 hours must be collected prior to the subsequent acalabrutinib dose (for trough PK sample).

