## **5 STUDY POPULATION**

Prospective approval of protocol deviations to recruitment and enrollment criteria, also known as protocol waivers or exemptions, is not permitted.

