### **5.1 Inclusion Criteria**

Participants are eligible to be included in the study only if **all** of the criteria below apply.

1. Participant or legally authorized representative must be able to understand the purpose and risks of the study and provide written informed consent and authorization to use protected health information (in accordance with national and local patient privacy regulations).

2. Male or female participants at least 18 years of age at the time of signing the informed consent.
3. Participants who are hospitalized with coronavirus (SARS-CoV-2) infection, confirmed by PCR test or other commercial or public health assay in any specimen, as documented by either of the following:
  - a) PCR positive in sample collected < 72 hours prior to first dose, OR
  - b) PCR positive in sample collected  $\geq$  72 hours prior to first dose (but no more than 14 days prior to first dose), documented inability to obtain a repeat sample (eg, due to lack of testing supplies, limited testing capacity, results taking > 24 hours, etc), AND progressive disease suggestive of ongoing SARS-CoV-2 infection.
4. Evidence of respiratory failure attributable to COVID-19 pneumonia (documented radiographically) before enrollment where respiratory failure is defined based on resource utilization of any of the following modalities:
  - a) Endotracheal intubation and mechanical ventilation.
  - b) Oxygen delivered by high-flow nasal cannula (heated, humidified, oxygen delivered via reinforced nasal cannula at flow rates > 20 L/min with fraction of delivered oxygen  $\geq$  0.5).
  - c) Noninvasive positive pressure ventilation or continuous positive airway pressure.
  - d) Extracorporeal membrane oxygenation.
5. Nasogastric tube or other types of oral or percutaneous gastric feeding tube; placement must be radiographically confirmed and expected to remain in place, as judged by the Investigator, for a minimum of 3 days after study enrollment.
6. Has received treatment with PPIs (eg, omeprazole, esomeprazole, lansoprazole, dexlansoprazole, rabeprazole, or pantoprazole) for a minimum of 24 hours immediately prior to enrollment; any PPI will be permitted, provided it meets the minimum equivalent daily dose of 20 mg rabeprazole.
7. Willing to follow contraception guidelines when discharged from the hospital (Appendix F).

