### **6.5.1 Premedications**

All participants must be receiving treatment with a PPI at the start of the study. Treatment with a PPI can begin at any time prior to enrollment, provided participants have received PPI

treatment for at least 24 hours prior to the first dose of acalabrutinib suspension. Any PPI is permitted, provided it meets the minimum equivalent daily dose of 20 mg rabeprazole.

Participants in the ICU may receive higher doses of PPI, and medications more appropriate for NG tube delivery, such as esomeprazole or lansoprazole. Higher doses of PPIs are allowed, if medically necessary. Please refer to Appendix H for equivalency charts.

If a participant no longer requires PPIs during the course of treatment, PPIs may be stopped. Please refer to treatment guidelines (Section 6.1.2) in such cases.

Any other premedication prior to treatment with acalabrutinib suspension is not necessary, but steroids as premedication for hypersensitivity reactions (eg, CT scan premedication) are allowed.

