**Table 9 Populations for Analysis**

Population/Analysis set	Description
PK Analysis Set	The PK Analysis Set will include all participants who received $\geq 1$ dose of acalabrutinib and had $\geq 1$ post-dose evaluable PK data point for acalabrutinib. The population will be defined by AstraZeneca, the pharmacokineticist, and the statistician prior to any analyses being performed.
Safety Analysis Set	The Safety Analysis Set will include all participants who received $\geq 1$ dose of study intervention
Efficacy Evaluable Set	The Efficacy Evaluable Set will include all participants who received $\geq 1$ dose of study intervention

ITT = intent to treat; PK = pharmacokinetic; PPI = proton-pump inhibitor.

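### Appendix H Table H17 lists lansoprazole 15 mg daily as an allowed ICU dose, but by Table H16 this is half the PPI minimum required at study start

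*Protocol*

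**What the plan says.** The entry rule is stated four times. Inclusion criterion 6 (Section 5.1) admits any PPI "provided it meets the minimum equivalent daily dose of 20 mg rabeprazole", and the same threshold appears in the synopsis (Section 1.1), Section 4.1 and Section 6.5.1. The synopsis and Section 4.1 fix when it applies: "Participants must be on this dosage of PPI at the start of the study". Both then allow weaning during the study. Section 5 adds: "Prospective approval of protocol deviations to recruitment and enrollment criteria, also known as protocol waivers or exemptions, is not permitted".

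Section 4.1 cites Appendix H next to the threshold. Section 6.5.1, after noting that ICU patients may be on larger doses, says: "Higher doses of PPIs are allowed, if medically necessary. Please refer to Appendix H for equivalency charts".

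Appendix H has two tables. Table H16 gives full, low and double doses for five PPIs. The text after it reads: "Proton-pump inhibitors listed in Table H17 may be used more frequently in the ICU setting and are allowed on study". Table H17, whose title also calls these PPIs allowed in intensive care, has a dose column, and its lansoprazole entry is "15 or 30 mg daily". No note ties Table H17 to the minimum.

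**The concern.** The two tables of the appendix give different answers about one dose. Table H16 classes lansoprazole 15 mg as a low dose, level with rabeprazole 10 mg. Table H17 presents it as allowed. Nothing in the protocol creates an ICU exception for a smaller starting dose: the only ICU allowance in Section 6.5.1 is upward, and enrolment criteria cannot be waived.

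The affected row is not a remote one. Section 6.5.1 names lansoprazole as one of two examples better suited to nasogastric delivery in the ICU. Criteria 4 and 5 require respiratory failure and a gastric feeding tube, so this describes the trial's own patients.

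The first primary objective is to characterise acalabrutinib PK when it is given with a PPI, and the minimum dose sets that condition at first dose. A participant who enters below it would be an eligibility deviation, yet no stated rule keeps the profile out of the primary summaries. Section 4.1 says: "Participants are considered evaluable if they have an evaluable PK profile, ie: (1) complete PK Visit 2 assessments; (2) receive active treatment", with a third condition about missing or incomplete data. Table 9 asks for at least one dose and at least one "post-dose evaluable PK data point for acalabrutinib". Neither mentions PPI dose. The timing rule for PK Visit 2 (Table 4) checks how long the PPI has been given, not how much.

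**Working it through.** **Inputs**

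- Minimum at study start: 20 mg rabeprazole equivalent per day (Section 5.1, criterion 6; Sections 1.1, 4.1 and 6.5.1).
- Full once-daily doses from Table H16: esomeprazole 20 mg, lansoprazole 30 mg, omeprazole 20 mg, pantoprazole 40 mg, rabeprazole 20 mg.
- Low once-daily doses from Table H16: lansoprazole 15 mg, omeprazole 10 mg, pantoprazole 20 mg, rabeprazole 10 mg.
- ICU daily doses from Table H17: esomeprazole 40 mg, lansoprazole 15 or 30 mg, omeprazole 20 to 40 mg, pantoprazole 40 mg.

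**The plan's own figure.** The 20 mg rabeprazole threshold is exactly the full/standard dose in Table H16, so the minimum amounts to one full dose per day.

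**Formula.** Rabeprazole equivalent = (Table H17 dose ÷ Table H16 full dose of the same drug) × 20 mg.

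| Table H17 dose | Calculation | Rabeprazole equivalent | Share of 20 mg minimum |
|---|---|---|---|
| Esomeprazole 40 mg | 40/20 × 20 | 40 mg | 200% |
| Lansoprazole 15 mg | 15/30 × 20 | 10 mg | 50% |
| Lansoprazole 30 mg | 30/30 × 20 | 20 mg | 100% |
| Omeprazole 20 mg | 20/20 × 20 | 20 mg | 100% |
| Omeprazole 40 mg | 40/20 × 20 | 40 mg | 200% |
| Pantoprazole 40 mg | 40/40 × 20 | 20 mg | 100% |

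Only lansoprazole 15 mg falls short.

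**Cross-check without assuming proportionality.** Matching by column in Table H16 gives the same answer. Lansoprazole 15 mg is in the low-dose column, where rabeprazole is 10 mg. Lansoprazole 30 mg, omeprazole 20 mg and pantoprazole 40 mg are in the full column, where rabeprazole is 20 mg. Esomeprazole 40 mg and omeprazole 40 mg are in the double column, where rabeprazole is 20 mg twice daily, or 40 mg per day.

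**After the correction.** With 15 mg removed, the Table H17 equivalents run from 20 to 40 mg, and all meet the minimum.

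**Weight of one case.** One below-minimum participant is 1/16 = 6.3% of the evaluable target, or 1/20 = 5.0% of the PK Analysis Set if all 20 enrolled enter it.

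**What cannot be computed.** The protocol gives no forecast of how many participants would start on 15 mg. Section 2.2.3.4 reports a PPI interaction at one dose only: omeprazole 40 mg once daily lowered acalabrutinib AUC by 42% and Cmax by 73%. One dose level gives no dose-response, so the effect of halving the PPI dose on exposure is unknown, all the more so for the suspension in cola.

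**The case against.** The strongest reply is that criterion 6 governs and an appendix table cannot relax it. The ban on waivers reinforces this. A site that looks up the equivalence as directed meets Table H16 first and sees 15 mg labelled a low dose. The sentence introducing Table H17 can also be read as allowing the drugs, with the dose column describing ICU practice. And being allowed on study covers the whole treatment period, when weaning to 15 mg is legitimate.

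The first part is right about which text prevails, but it does not make Table H17 correct. Appendix H is where the protocol sends sites to apply the criterion, and Table H17 carries no caveat. The drugs-only reading is strained for a table with a dose column. The point about weaning stands and limits the conflict to entry.

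The second line of reply is that the consequence is small. The sponsor, pharmacokineticist and statistician define the PK Analysis Set before analysis (Table 9). Section 9.4.1 permits a sensitivity analysis without significant protocol deviations. PK is summarised without formal testing (Section 9.4.2). Section 9.2 already expects PPI use to vary, and PK Visit 2 may fall after weaning has begun. All of this holds and keeps the point modest. These safeguards are discretionary, however, and act only after an ineligible participant has been enrolled.

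**Conclusion.** The point holds. Table H17 allows a lansoprazole dose equal to 10 mg rabeprazole, 50% of the required starting minimum by the protocol's own equivalence table, and it is the only dose in Table H17 below that minimum. It is an error in an operational table that sites are told to use when applying an eligibility threshold tied to the primary PK condition, and it should be corrected.

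The conclusion rests on Table H16 as the equivalence standard and on reading the Table H17 dose column as doses that may be used. It applies at study start only. It does not invalidate the primary PK analysis: the number of participants affected and the effect on exposure are both unknown, and each affected participant would make up about 5% to 6% of the PK data.

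**What to change.** Either of these is enough:

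- Remove the 15 mg option from Table H17, so that the lansoprazole entry is 30 mg daily.
- Keep the entry and add a footnote that Table H17 doses remain subject to criterion 6 at study start, so that lansoprazole 15 mg is acceptable only once weaning has begun.

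The cost is one table cell or one footnote. Optionally, flag in the PK summary any participant whose PPI dose was below the minimum at first dose. This needs no new data collection, because Section 6.5 already has dose, frequency and dates recorded for every concomitant medication.
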